### 4.3 Rationale for the Dose Selected

Dose selection for the treatment of unresectable or metastatic GIST patients with avapritinib was based on a 3+3 dose escalation study design with a starting dose of 30 mg QD (BLU-285-1101). Forty-six patients were enrolled in Part 1 (dose escalation) of the study, 23 patients with PDGFR $\alpha$ -mutated GIST and 23 patients with KIT-mutated GIST, treated with avapritinib at doses of 30 to 600 mg.

Preliminary data showed avapritinib to be well tolerated at QD doses of 30 mg to 400 mg. No DLTs were reported at doses ranging from 30 mg to 400 mg; 2 DLTs were observed at 600 mg, including Grade 2 hypertension, Grade 2 rash, and Grade 2 memory impairment in 1 patient and Grade 2 hyperbilirubinemia in the other patient in Study BLU-285-1101.

After a single dose and repeat dosing of avapritinib, systemic exposure was dose proportional over the dose range of 30 to 400 mg QD. The steady state (C1D15) geometric mean  $C_{max}$  (%CV) of avapritinib at doses of 300 and 400 mg QD was 774 ng/mL (49.4%) and 1009 ng/mL (50.9%), respectively, and the corresponding  $AUC_{0-\tau}$  was 14074 h•ng/mL (45.1%) and 20298 h•ng/mL (41.5%). The mean accumulation ratio after repeat dosing of avapritinib (dose range: 30 – 400 mg QD) was 3.4 – 5.2.

On 14 February 2017, the maximum tolerated dose for the BLU-285-1101 study was determined to be 400 mg QD and the dose expansion (Part 2) phase of the study started to enroll patients at this dose. Subsequently, based on a joint Investigator and Sponsor review of the available safety, PK/pharmacodynamics, and clinical activity data observed across all cycles of treatment during Part 1 (dose escalation) and Part 2 (dose expansion), 300 mg QD was selected as the avapritinib starting dose for the remainder of Part 2.

Exposures in humans who have received avapritinib at 300 mg and 400 mg QD doses are active against resistance mutations in patient-derived xenograft models showing an overlap covering a broad range of KIT mutations, including exon 11/13 and exon 17/18. Hence, 300 mg PO QD is expected to be clinically active and well tolerated.

As of this 11 October 2017 data cut, 43 patients had initiated treatment in the dose expansion part (Part 2) of the study at 400 mg QD and 27 patients initiated at 300 mg QD.

## 5 POPULATION

### 5.1 Number of Patients

Approximately 460 patients will be enrolled and randomized in a 1:1 ratio, stratified by TKI treatment (third vs. fourth), geographic region (Asia vs. rest of the world), and mutation status (PDGFR $\alpha$  D842V mutation present vs. absent) including:

- Approximately 230 patients randomized to receive avapritinib (Arm A).
- Approximately 230 patients randomized to receive regorafenib (Arm B).

At least 70% of the patients enrolled should be receiving their third distinct TKI treatment for GIST, ie, no more than 30% of patients should be receiving their fourth distinct TKI treatment for GIST. Enrollment will be restricted to include only patients receiving their third distinct TKI once 30% of the targeted 460 patients who are receiving their fourth distinct TKI treatment have been enrolled.

### 5.2 Inclusion Criteria

Patients meeting the following criteria will be eligible for participation in the study:

1. Patients who are  $\geq 18$  years of age.
2. Patients who have histologically confirmed metastatic or unresectable GIST. Unresectable GIST must be confirmed to be unresectable by a qualified surgeon.
3. Patients who have received imatinib and 1 or 2 other TKIs for the treatment of GIST, including TKIs used for adjuvant therapy. Each different TKI is counted once regardless of how often it was used, and if 2 different TKIs are used in combination, both TKIs are counted. Patients must have disease progression prior to enrollment. Prior use of other systemic and local therapies is not restricted.
4. Patients who have an ECOG PS of 0 to 1.
5. Patient, or legal guardian if permitted by local regulatory authorities, who provides informed consent to participate in the study.

### 5.3 Exclusion Criteria

Patients meeting any of the following criteria will not be eligible for participation in the study:

1. Patients who have received prior treatment with avapritinib or regorafenib.
2. Patients who have previously received more than 3 different TKIs for the treatment of GIST, including TKIs used for adjuvant therapy. Each different TKI is counted once

- regardless of how often it was used, and if 2 different TKIs are used in combination, both TKIs are counted.
3. Patients who are known to be both KIT and PDGFR $\alpha$  wild type.
  4. Patients who received any systemic anticancer therapy within 1 week before the first dose of study drug. Prior radiotherapy (including stereotactic radiotherapy) to major organs within 2 weeks of the first dose of study drug, or focal radiotherapy (including stereotactic radiotherapy), such as to bones, limbs, or other areas not involving major organs, within 3 days.
  5. Patients who have clinically significant, uncontrolled, cardiovascular disease, including congestive heart failure Grades II, III or IV according to the New York Heart Association classification, myocardial infarction or unstable angina within the previous 6 months, or uncontrolled hypertension.
  6. Patients who have experienced arterial thrombotic or embolic events such as cerebrovascular accident (including transient ischemic attacks) within 6 months before the first dose of study drug, or venous thrombotic events such as pulmonary embolism or deep vein thrombosis within 14 days before the first dose of study drug. Patients with venous thrombotic events such as pulmonary embolism or deep vein thrombosis  $\geq$  14 days before the first dose of study drug are not excluded provided they are on stable doses of anti-coagulation, or have completed the planned anti-coagulation regimen.
  7. Patients who have experienced any hemorrhage or bleeding event NCI CTCAE version 5.0 Grade 3 or higher within 4 weeks before the first dose of study drug.
  8. Patients who have a known risk of intracranial bleeding, such as a brain aneurysm that has not been removed or repaired, or a history of intracranial bleeding within 1 year prior to the first dose of study drug.
  9. Patients who have a symptomatic non-healing wound, ulcer, gastrointestinal perforation, or bone fracture.
  10. Patients who have poor organ function as defined by one or more of the following laboratory parameters:
    - Persistent proteinuria of NCI CTCAE version 5.0 Grade 3 or higher
    - Alanine aminotransferase and AST  $> 3 \times$  upper limit of normal (ULN) if no hepatic metastases are present;  $> 5 \times$  ULN if hepatic metastases are present.
    - Total bilirubin  $> 1.5 \times$  ULN; and in presence of Gilbert's syndrome, total bilirubin  $> 3 \times$  ULN or direct bilirubin  $> 1.5 \times$  ULN.
    - Estimated (per institutional standard; eg, Cockcroft-Gault formula or Modification of Diet in Renal Disease equation) or measured creatinine clearance

- < 40 mL/min (if the estimated or measured creatinine clearance is  $\geq$  40 mL/min using any of these methods the patient is not excluded).
- Platelet count  $< 90 \times 10^9/L$  and absolute neutrophil count (ANC)  $< 1.0 \times 10^9/L$ .
  - Hemoglobin  $< 9$  g/dL. Transfusion and erythropoietin may be used to reach at least 9 g/dL, but must have been administered at least 2 weeks before the first dose of study drug.
11. Patients who have received neutrophil growth factor support within 14 days of the first dose of study drug.
  12. Patients who require therapy with a concomitant medication that is a strong inhibitor or strong or moderate inducer of CYP3A4.
  13. Patients who have had a major surgical procedure (minor surgical procedures such as central venous catheter placement, tumor needle biopsy, and feeding tube placement are not considered major surgical procedures) within 14 days of the first dose of study drug. Patient has significant traumatic injury within 28 days before the first dose of study drug.
  14. Patients who have a history of another primary malignancy that has been diagnosed or required therapy within 3 years before the first dose of study drug. The following prior malignancies are not exclusionary: completely resected basal cell and squamous cell skin cancer, curatively treated localized prostate cancer, and completely resected carcinoma in situ of any site. Patients with a prior or concurrent malignancy whose natural history or treatment does not have the potential to interfere with the safety or efficacy assessment of the investigational agent may be included after approval by medical monitor.
  15. Patients who have a history of a seizure disorder requiring anti-seizure medication.
  16. Patients who have metastases to the brain.
  17. Patients who are unwilling or unable to comply with scheduled visits, drug administration plan, laboratory tests, or other study procedures and study restrictions.
  18. Patients who have a QT interval corrected using Fridericia's formula (QTcF) of  $> 450$  msec.
  19. Women who are unwilling, if not postmenopausal or surgically sterile, to abstain from sexual intercourse or employ highly effective contraception from the time of the first dose of study drug and for at least 60 days after the last dose of study drug. Men who are unwilling, if not surgically sterile, to abstain from sexual intercourse or employ highly effective contraception from the time of the first dose of study drug and for at least 90 days after the last dose of study drug. Refer to [Section 6.6.2](#) for acceptable methods of contraception.

20. Women who are pregnant, as documented by a serum beta human chorionic gonadotropin ( $\beta$ -hCG) pregnancy test consistent with pregnancy, obtained within 7 days before the first dose of study drug. Females with  $\beta$ -hCG values that are within the range for pregnancy but are not pregnant (false-positives) may be enrolled with written consent of the Sponsor, after pregnancy has been ruled out. Females of non-childbearing potential (postmenopausal for more than 1 year; bilateral tubal ligation; bilateral oophorectomy; hysterectomy) do not require a serum  $\beta$ -hCG test.
21. Women who are breastfeeding.
22. Patients who have prior or ongoing clinically significant illness, medical condition, surgical history, physical finding, or laboratory abnormality that, in the Investigator's opinion, could put the patient at an unacceptably high risk for toxicities, or alter the absorption, distribution, metabolism, or excretion of the study drug; or impair the assessment of study results.
23. Patients with a known hypersensitivity to avapritinib, regorafenib, or the excipients in either study drug.

#### **5.4 Patient Identification and Registration**

Patients who are candidates for enrollment into the study will be evaluated for eligibility by the Investigator to ensure that the inclusion and exclusion criteria (see [Section 5.2](#) and [Section 5.3](#)) have been satisfied.

Upon identification of an eligible patient, study centers will submit a request to the Sponsor or designee to register each patient for enrollment. Further instructions will be provided in the study manual.

The Medical Monitor or designee will confirm eligibility for all patients before randomization and administration of the first dose of study drug.

#### **5.5 Randomization**

Patients who meet all study eligibility criteria will be randomly assigned in a 1:1 ratio to receive avapritinib PO QD or regorafenib PO QD, stratified by TKI treatment (third vs. fourth), geographic region (Asia vs. rest of the world), and mutation status measured in ctDNA or a tumor sample (PDGFR $\alpha$  D842V mutation present vs. absent).

At least 70% of the patients enrolled in this study should be receiving study treatment as their third distinct TKI treatment for GIST, ie, no more than 30% of patients should be receiving their fourth distinct TKI treatment for GIST. Enrollment will be restricted to include only patients receiving their third distinct TKI treatment once 30% of the enrolled targeted 460 patients who are receiving their fourth distinct TKI treatment have been enrolled.

The randomization assignment will be implemented by an interactive web response system (IWRS).

## 5.6 Study Completion

It is anticipated that patients will receive at least 1 cycle of avapritinib or regorafenib; no maximum treatment duration has been set. After C1, patients may continue to receive study drug until precluded by toxicity, or until disease progression, noncompliance, pregnancy, withdrawal of consent, death, physician decision, or closure of the study by the Sponsor. Patients permanently withdrawn from study participation will not be allowed to re-enter the study.

Patients will be considered to have completed the study if they withdraw from the study for any of the criteria listed in [Section 5.7](#).

## 5.7 Patient Withdrawal Criteria

Patients have the right to withdraw from the study at any time for any reason.

Patients must withdraw or be withdrawn from study treatment for any of the following reasons:

- Withdrawal of consent
- Pregnancy
- Death

Patients may withdraw or be withdrawn from study treatment for any of the following reasons:

- AE
- Disease progression
- Protocol deviation
- Investigator decision
- Loss to follow-up

When a patient discontinues study drug or withdraws from the survival follow-up part of the study, the primary reason(s) for discontinuation or withdrawal must be recorded in the appropriate sections of the electronic case report form (eCRF) and all efforts will be made to complete and report final study observations as thoroughly as possible.

All related AEs should be monitored until they are resolved, have stabilized, have returned to pre-exposure baseline, are determined to be due to another illness, or until a subsequent therapy is initiated. For AEs considered not related to study drug, similar monitoring guidelines will only be required through 30 days after the last dose of study drug. If the patient withdraws from treatment because of an AE, every effort must be

made to perform protocol-specified safety follow-up procedures, as outlined in [Section 7.6](#).

In the event a patient is withdrawn from study drug or the follow-up part of the study, the Medical Monitor must be informed. If there is a medical reason for withdrawal, the patient will remain under the supervision of the Investigator or designee until the condition has returned to baseline or stabilized.

## 6 STUDY CONDUCT

### 6.1 General Conduct

The study will be conducted at multiple centers in North America, Europe, Australia, and Asia.

This study will be conducted in compliance with the protocol, Good Clinical Practice (GCP), and the applicable regulatory requirements.

Patients may be randomized in the system at any time but must be dosed within 28 days of signing of informed consent.

The schedule of assessments for the study is provided in [Table 2](#).

The minimum duration of patient participation is expected to be approximately 3 months, including a screening period to assess study eligibility up to 4 weeks (28 days); a treatment period of at least 1 cycle (28 days); an EOT visit at least  $14 \pm 7$  days after the last dose of study drug; and a Safety Follow-up visit in the clinic for physical examination and resolution of any AEs 30 days ( $\pm 7$  days) after the last dose of study drug. Thereafter, patients are to be followed for tumor imaging every 8 weeks ( $\pm 7$  days) until disease progression, death, initiation of new anti-GIST therapy, withdrawal of consent, or closure of the study by the Sponsor and then survival approximately every 2 months until death, withdrawal of consent or closure of the study by the Sponsor.

The end of the study is defined as the time that the last patient completes his/her last visit (LPLV), including assessments performed as part of PFS follow-up, if the patient enters the PFS follow-up part of the study. See [Section 7](#) for details of all study assessments.

The expected enrollment period is approximately 18 months and the expected duration of the study to reach the primary analysis timepoint is approximately 24 months until a total number of 264 PFS events are reached. The study will be completed when all patients are no longer receiving study drug and follow-up for OS has been concluded.

### 6.2 Early Termination

The study may be terminated early at the discretion of the Sponsor, if there is sufficiently reasonable cause. In the event of such action, written notification documenting the reason for study termination will be provided to each Investigator.

Circumstances that may warrant early termination include, but are not limited to:

- Determination of unexpected, significant, or unacceptable risk to patients.
- Insufficient adherence to protocol requirements.
- Plans to modify, suspend, or discontinue the development of study drug.
- Other administrative reasons.

Should the study be terminated prematurely, all study materials must be returned to the Sponsor or Sponsor's designee.

### **6.3 Dose and Administration**

Avapritinib will be administered PO at a starting dose of 300 mg QD in continuous 28-day cycles.

Prespecified dose modifications guidance for AEs related to avapritinib including cognitive effects, are described in [Section 6.3.1](#).

Regorafenib will be administered at 160 mg PO QD for 21 days in 28-day cycles with 1 week off therapy. Doses of avapritinib or regorafenib may be modified or discontinued for toxicity as described in [Section 6.3.1](#).

Patients receiving regorafenib who experience disease progression may be offered the opportunity to cross over to the avapritinib treatment arm after evaluation and confirmation of disease progression by central radiology review and a washout period of 7 to 28 days after their last dose of regorafenib; see [Section 7.6](#) for additional details. Prespecified dose modifications guidance for AEs related to regorafenib including hand-foot skin reaction, hypertension, and AST, ALT, or bilirubin increases are described in [Section 6.3.1](#).

Patients will be dispensed the appropriate number of Sponsor-packaged, labeled bottles on D1 of each cycle to allow dosing until D1 of the next cycle, which is expected to be within 28 or 56 days. Patients must return all unused tablets (or the empty bottles) at each scheduled visit.

Avapritinib doses should be administered with a glass of water (at least 8 ounces or 250 mL) in a fasted state, with no food intake from 2 hours before until 1 hour after study drug administration. Patients should be instructed to swallow tablets whole and to not chew the tablets. Antacids should not be taken within 3 hours before or after study drug administration.

Regorafenib will be provided as 40 mg strength tablets and it should be administered after a low-fat meal. See [Appendix 1](#) for additional details.

Avapritinib or regorafenib should be administered QD at approximately the same time each day. If a patient forgets to take his/her daily dose in the morning, he/she should take that dose by 4 pm that day. If the dose has not been taken by 4 pm, then that dose should be omitted, and the patient should resume treatment with the next scheduled dose.

If the patient forgets to take his/her daily dose in the evening, he/she should take the study drug dose by 12 am (midnight) that day, and at least 8 hours before the next dose. If the dose has not been taken by the specified times, that dose should be omitted, and the patient should resume treatment with the next scheduled dose.

If a patient vomits during or after taking avapritinib or regorafenib, re-dosing is not permitted until the next scheduled dose.

A temporary discontinuation, up to 56 days (8 weeks) in avapritinib or regorafenib dosing is allowed for patients who require an interruption (eg, for surgery or another interventional procedure) during the treatment period. Avapritinib should be discontinued 48 hours before the procedure (unless the procedure is required more urgently) and resumed at least 48 hours after the procedure is completed. For regorafenib, a vascular endothelial growth factor receptor inhibitor that can impair wound healing, treatment should be stopped at least 2 weeks before the procedure, if possible, and at least 1 week before the procedure, unless the procedure is required more urgently. The decision to resume regorafenib after surgery should be based on clinical judgment of adequate wound healing.

### **6.3.1 Dose Modification Recommendations for Adverse Events**

Dose modification guidelines are summarized for avapritinib in [Table 1](#), and for regorafenib in [Appendix 2](#). These guidelines should be followed by clinical Investigators; however, for an individual patient, dose interruptions, reductions, and treatment discontinuation should also be based on the clinical circumstance. Deviation from these guidelines must be documented and communicated with the sponsor.

Adverse events are to be graded according to NCI CTCAE version 5.0. When the observed toxicity has resolved to  $\leq$  Grade 2 or returned to baseline, the investigator may resume dosing if clinically indicated. Guidance for re-escalation after resolution of adverse drug reactions is provided in [Section 6.3.2](#).

Avapritinib dose reductions to below 100 mg QD are not permitted (see [Table 1](#)), and regorafenib dose reductions to below 80 mg QD are not permitted (See [Appendix 2](#)). If a patient requires dose reduction below these dose levels, study treatment should be discontinued.

Doses may be interrupted for study-drug related toxicities for up to 56 days (8 weeks). In general, if a study drug-related toxicity does not resolve to  $\leq$  Grade 2 or has not returned to baseline after dose interruption for more than 56 days, the patient must be discontinued from study treatment unless after discussion with the medical monitor, resumption of treatment is considered to be in the best medical interest of the patient, and this is documented in writing. Additionally, the Sponsor's medical monitor must be contacted if

an AE deemed unrelated to treatment requires a dose interruption for more 56 days; a longer recovery period is permitted with written approval by the Sponsor.

During dose interruptions, study sites should continue to observe the study schedule as planned.

Once adverse drug reactions have resolved after the guidelines below are followed, Investigators are encouraged to re-escalate the dose of study drug as described in [Section 6.3.2](#).

**Table 1: Dose Modification and Re-escalation Guidelines for Avapritinib-Related Toxicity**

Toxicity	Modification
General	
Grade 1 or Grade 2	
 
No dose modification required
 

Grade 3 - 4	
 
Occurrence: Hold until event is <math>\leq</math> Grade 2, or has returned to baseline, and then resume by reducing the dose by 100 mg less than the current dose 
 

 
 
 
Occurrence at 100 mg: Discontinue avapritinib 
 

 
 
 

Cognitive or Mood Effects	
Grade 1 with only minor impairment	No dose modification required
Grade 1, other than minor impairment	
 
Interrupt dosing for 7 days, and resume dosing without dose reduction
 
The dosing interruption may be repeated if the impairment continues to worsen after resuming dosing; however, repeated dosing interruption is at the discretion of the investigator, and should be balanced with the need to treat the underlying GIST
 

Grade 2	
 
Interrupt dosing for a minimum of 7 days
 
Resume dosing with a dose reduction of 100 mg when the cognitive effect has improved to Grade 1 or less, or still at Grade 2, if continued treatment is considered in the best medical interest of the patient due to the underlying GIST
 
If the patient is already receiving a dose of 100 mg QD, and continued treatment is considered in the best medical interest of the patient due to the underlying GIST, treatment may be resumed at 100 mg
 

Grade 3-4	
 
Interrupt dosing for a minimum of 14 days
 
Resume dosing with a dose reduction of 100 mg when the cognitive effect has improved to Grade 1 or less, or when it has improved to Grade 2, if continued treatment is considered in the best medical interest of the patient due to the underlying GIST
 
Occurrence at 100 mg: Discontinue avapritinib
 

Intracranial Bleeding	
Grade 1	
 
Interrupt dosing for a minimum of 7 days, and re-image the brain
 

	
 
Resume dosing without dose reduction, if the bleed is stable or improving, and continued treatment is considered in the best medical interest of the patient due to the underlying GIST
 

Grade 2	
 
Interrupt dosing for a minimum of 14 days and re-image the brain
 
Resume dosing with a dose reduction of 100 mg when the intracranial bleeding has improved to Grade 1 or less, or still at Grade 2, if continued treatment is considered in the best medical interest of the patient due to the underlying GIST
 
Occurrence at 100 mg: Discontinue avapritinib
 

Grade 3-4	
 
Discontinue avapritinib
 

Abbreviations: CNS = central nervous system; GIST = gastrointestinal stromal tumor; QD = once daily.

 Changes in cognition, memory, attention, mood, or speech (thought to originate in the CNS).

 If avapritinib treatment is resumed after interruption for a cognitive or mood effect, or for an intracranial bleeding event, the investigator must document in writing that resuming avapritinib treatment was considered to be in the best medical interest of the patient.

For regorafenib, dose modification is described in [Appendix 2](#).

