Treatment with avapritinib has been well tolerated in patients with GIST. Most AEs have been Grade 1 or 2 in intensity, with the most common ( $\geq 25\%$ ) including nausea (56%), fatigue (53%), periorbital edema (43%), vomiting (41%), peripheral edema (34%), anemia (31%), diarrhea (31%), cognitive effects (consisting of multiple similar AEs aggregated into a single category [30%]), increased lacrimation (30%), and decreased appetite (28%). There were no DLTs until the 600 mg dose cohort was reached and DLTs were noted in 2 patients: 1 patient experienced Grade 2 hypertension, Grade 2 rash, and Grade 2 memory impairment; the other patient experienced Grade 2 hyperbilirubinemia. The maximum tolerated dose was determined to be 400 mg QD.

Overall, 49 patients discontinued avapritinib treatment. Six patients discontinued due to AEs, 40 patients discontinued due to disease progression, and 3 patients discontinued avapritinib due to patient's decision.

The single dose (Cycle 1 Day 1; C1D1) and steady state (Cycle 1 Day 15; C1D15) pharmacokinetics of avapritinib have been evaluated in Study BLU-285-1101. Preliminary unaudited PK data from the 11 April 2018 datacut are presented. After administration of single oral doses of avapritinib ranging from 30 to 400 mg avapritinib, the median time to peak concentration ( $T_{max}$ ) ranged from 2 to 4 hours postdose, and the mean plasma elimination half-life of avapritinib ranged from 35 hours to 57 hours. After a single dose and repeat dosing of avapritinib, systemic exposure was dose proportional over the dose range of 30 mg to 400 mg QD. The steady state (C1D15) geometric mean  $C_{max}$  (%CV) of avapritinib at doses of 300 mg QD and 400 mg QD was 774 ng/mL (49.4%) and 1009 ng/mL (50.9%), respectively, and the corresponding area under the plasma concentration-time curve ( $AUC_{0-\tau}$ ) was 14074 h•ng/mL (45.1%) and 20298 h•ng/mL (41.5%), respectively. The mean accumulation ratio after repeat dosing of avapritinib (dose range: 30 – 400 mg QD) was 3.4 – 5.2. Based on the data collected thus far, and the exposures required for antitumor activity in GIST patient-derived xenograft models (Figure 2), systemic exposure at 300 mg QD - 400 mg QD is predicted to provide broad coverage of the primary (eg, exon 11) and secondary KIT (eg, exon 11/17 and exon 11/13) mutations.

[figure not shown]
**Figure 2: Clinical Exposure of Avapritinib Reaches Levels Projected to be Efficacious Across Multiple KIT-mutant Genotypes**

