### 6.3.2 Dose Re-escalation After Resolution of Adverse Drug Reactions

Avapritinib and regorafenib doses may be re-escalated from the reduced dose level to the immediate previously administered dose level if any of the following criteria are met:

- All  $\geq$  Grade 2 non-hematologic (other than CNS toxicities) have recovered to  $<$  Grade 2 for at least 2 weeks.
- All  $\geq$  Grade 3 hematologic toxicities have recovered to  $\leq$  Grade 2 and are manageable with supportive therapy.
- All  $\geq$  Grade 2 CNS toxicities have recovered to  $\leq$  Grade 1 and are manageable with supportive therapy.

Patients may receive step-wise avapritinib dose re-escalations up to 300 mg QD (eg, 100 mg QD to 200 mg QD to 300 mg QD) if the above criteria continue to be met.

Patients may receive step-wise regorafenib dose escalations up to 160 mg QD (eg, 80 mg QD to 120 mg QD to 160 mg QD) if the above criteria continue to be met.

A patient should be treated and tolerate therapy well for at least 1 cycle at each higher dose level before the dose is escalated again. In no circumstances should a patient receive a dose higher than 300 mg QD.

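### After a CNS event, Protocol 6.3.2 lets avapritinib return to the previous dose at the same grade that allowed the reduced restart, with no minimum time at the reduced dose

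*Protocol*

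**What the plan says.** Protocol Table 1 holds avapritinib for at least 7 days after a Grade 2 cognitive or mood effect, and for at least 14 days after a Grade 3–4 cognitive or mood effect or a Grade 2 intracranial bleed. The restart rule for the cognitive effects is "Resume dosing with a dose reduction of 100 mg when the cognitive effect has improved to Grade 1 or less", and for the bleed "Resume dosing with a dose reduction of 100 mg when the intracranial bleeding has improved to Grade 1 or less". Restart at Grade 2 is also possible where the investigator judges it in the patient's best interest.

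Section 6.3.2 allows a step up "from the reduced dose level to the immediate previously administered dose level" when any one of three listed criteria is met:

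- The first bullet covers toxicities of at least "Grade 2 non-hematologic (other than CNS toxicities) have recovered to" below Grade 2, and requires that recovery to have lasted 2 weeks.
- The hematologic bullet gives no duration.
- The CNS bullet requires events of Grade 2 or higher to have recovered to at most "Grade 1 and are manageable with supportive therapy". It gives no duration.

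A later sentence requires the patient to "tolerate therapy well for at least 1 cycle at each higher dose level before the dose is escalated again". Section 6.3.1 adds that, once reactions have resolved, "Investigators are encouraged to re-escalate the dose of study drug" in the way 6.3.2 describes.

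**The concern.** The grade that allows a restart at the lower dose is also the grade that allows a return to the higher one. Nothing in the text requires the lower dose to be tried for any period in between.

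A patient who reached Grade 1 during the hold did so off drug. That status does not show that the reduced dose is tolerated. For cognitive effects it is plausible that the improvement partly reflects washout. The reduction could then be reversed before exposure at the lower dose is near steady state, and so before it has been tested.

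The stake is patient safety. Cognitive effects and intracranial bleeding are the two categories of adverse events of special interest in SAP 4.7.2. Protocol 1.2.3.1 reports cognitive effects in 30% of Phase 1 patients, and 1.2.2.3 reports CNS effects, including brain hemorrhage, as dose limiting in dogs.

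**Working it through.** **Step 1: follow one patient through the text.** A patient on 300 mg has a Grade 2 cognitive effect. Dosing stops for at least 7 days, the event improves to Grade 1, and Table 1 restarts at 200 mg. The same Grade 1 status already meets the grade part of the CNS bullet in 6.3.2. If the investigator judges the event manageable, 300 mg is permitted. The stated minimum time at 200 mg is none.

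**Step 2: look for another rule that sets a minimum.**

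| Rule | Does it set time at the reduced dose before the first step up? |
|---|---|
| 2-week recovery, 6.3.2 first bullet | No. CNS toxicities are excluded, and it counts recovery time, not time at the reduced dose |
| One cycle at each higher level, 6.3.2 | No. It binds only a second step, for example 100 to 200 mg and then to 300 mg |
| 7- or 14-day hold and re-imaging, Table 1 | No. These precede the restart |
| Written justification, Table 1 footnote 2 | No. It covers resuming, not stepping up |
| SAE reporting of all intracranial bleeds, 9.1.3 | No. It does not govern dosing |
| Brain imaging at Weeks 12 and 24, Table 2 | No. It is not tied to the dose change |

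**Step 3: the opening sentence of 6.3.2.** Any one criterion is enough. Take a patient reduced for a CNS event who also had a non-hematologic, non-CNS toxicity that has been below Grade 2 for 2 weeks. Read literally, the first bullet permits the step up whether or not the CNS bullet is met. Amending the CNS bullet alone would not close the gap.

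**Step 4: who is in scope.** Only patients above 100 mg are affected. At 100 mg, a Grade 2 cognitive event may resume at 100 mg, while a Grade 3–4 cognitive event or a Grade 2 bleed stops treatment. Grade 3–4 bleeds stop treatment at any dose, and Grade 1 CNS events carry no reduction.

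**Step 5: exposure.** Inputs are from Protocol 1.2.3.1. "The mean accumulation ratio after repeat dosing of avapritinib" was 3.4 to 5.2, and the single-dose half-life was 35 to 57 h. Assume linear first-order kinetics and once-daily dosing.

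With accumulation ratio R, the share left after 24 h is q = 1 − 1/R:

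- R = 3.4: q = 0.7059, half-life 47.8 h.
- R = 5.2: q = 0.8077, half-life 77.9 h.

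Drug remaining after the hold:

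- 7 days: q^7 = 8.7% and 22.4%. From the single-dose half-lives, 0.5^(168/35) = 3.6% and 0.5^(168/57) = 13.0%.
- 14 days: q^14 = 0.8% and 5.0%. From the single-dose half-lives, 0.5^(336/35) = 0.13% and 0.5^(336/57) = 1.7%.

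Share of reduced-dose steady-state exposure on day n after restart:

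| Basis | Day 1 | Day 7 | Day 14 |
|---|---|---|---|
| R = 3.4, no residual drug: 1 − q^n | 29.4% | 91.3% | 99.2% |
| R = 5.2, no residual drug: 1 − q^n | 19.2% | 77.6% | 95.0% |
| R = 3.4, residual after 7-day hold, 300 to 200 mg: 1 − q^n(1 − 1.5q^7) | 38.7% | 92.4% | 99.3% |
| R = 5.2, same formula | 46.4% | 85.1% | 96.7% |
| Half-life 35 h, no residual drug | 37.8% | 96.4% | 99.9% |
| Half-life 57 h, no residual drug | 25.3% | 87.0% | 98.3% |

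The two bases do not agree exactly. Half-lives of 35 and 57 h would give R = 1/(1 − 0.6217) = 2.6 and 1/(1 − 0.7469) = 3.95, below the reported 3.4 to 5.2. Both are therefore shown.

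**The case against.** The best defence is that CNS events already get the stricter package. General toxicities are reduced only at Grade 3–4, have no fixed minimum hold, and may restart at Grade 2. Cognitive events are held and reduced from Grade 2, with fixed holds. Bleeds add re-imaging and earlier discontinuation, and resuming needs written justification. A fixed hold in place of a fixed time at the lower dose is a coherent choice and may be deliberate. Re-escalation is permitted, not required, and manageability is a real clinical judgement. All of this stands, but none of it sets a time at the reduced dose.

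Four further points limit what can be claimed:

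- The 2-week rule for other non-hematologic toxicities counts recovery time, which can run during a hold. It lends a length for the fix, but is not a like-for-like precedent. The hematologic bullet has no duration either.
- No part of the documents gives the time course of cognitive recovery, and nothing links improvement of a bleed to plasma level. Washout is an inference for the former and is not shown for the latter.
- With residual drug counted, exposure is already 85–92% of steady state by day 7, so kinetics alone would support about one week. The inputs are ranges of dose-level means, and between-patient variation is wide (AUC CV 45.1% at 300 mg).
- Time at a lower dose may cost efficacy.

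A reader might also infer that a patient can go back to the full dose on day 7 or 14, that the two sections contradict each other, or that CNS events break a rule applied elsewhere. The documents support none of these. The patient must first restart at the reduced dose. Table 1 governs restart and 6.3.2 governs re-escalation. The regorafenib rules in Appendix 2 are themselves mixed: fixed waits for hypertension and liver tests, none for general toxicities or hand-foot skin reaction.

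**Conclusion.** The gap is real but narrow. For patients above 100 mg whose dose was cut after a Grade 2–4 cognitive or mood effect or a Grade 2 intracranial bleed, 6.3.2 allows the cut to be reversed once the event is Grade 1 or less and manageable. It states no minimum time at the reduced dose, and its any-one-criterion wording could, read literally, bypass the CNS bullet. Patients restarted at Grade 2 come into scope under the CNS bullet only when they reach Grade 1.

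The exposure figures show how far the reduced dose has been tested by a given day, under linear kinetics. They do not show a higher rate of recurrence. The number of patients affected cannot be derived from the documents. Power and alpha are untouched. This is a cheap improvement for patient safety, not an error in the trial's inference.

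**What to change.** Make two changes to 6.3.2.

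1. Replace the any-one-criterion opening with wording that every criterion applicable to the toxicity that led to the reduction must be met.
2. Amend the CNS bullet to: *All Grade 2 or higher CNS toxicities, including Grade 2 intracranial bleeding, have recovered to Grade 1 or less, are manageable with supportive therapy, and have remained at Grade 1 or less for at least 2 weeks of treatment at the reduced dose before the first step up.*

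Two weeks is a judgement. It matches a length 6.3.2 already uses and brings exposure to 95–99% of the reduced-dose steady state on the accumulation-ratio basis. A longer period, such as one cycle, is for the medical team to decide.

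The cost is a short amendment, a letter to sites, and up to about 2 more weeks at a reduced dose for some patients, against interruptions of up to 56 days that 6.3.1 already allows. There may be a small efficacy cost. In Phase 1, KIT-mutant patients had a median PFS of 11.5 months at 300 mg or more and 2 months at 30–200 mg. That comparison is non-randomised and contrasts dose groups, not a two-week delay. It is a reason to keep the period short.
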